Dry eye is a common public health problem with an estimated 25 million Americans affected by this condition (1). It is a chronic, possibly progressive inflammatory condition that leads to symptoms of ocular discomfort as well as blurred vision (2). Regardless of the underlying etiology, dry eye has been shown to be associated with abnormalities in the pre-corneal tear film and subsequent inflammatory changes in the entire ocular surface including the adnexa, conjunctiva and cornea (3). Since the recognition of the role of inflammation in dry eye, a number of anti-inflammatory treatments have been investigated designed to inhibit various inflammatory pathways. Previously loteprednol etabonate 0.5% and dexamethasone 0.1% drops have been shown to improve ocular surface inflammation and benefit patients with dry eye (4-7).

1.2 Rationale

Previous studies showed that dexamethasone and loteprednol topical drops have led to favorable results (4-7). However, the requirement of frequent instillation of drops by the patients is problematic causing discomfort and blurring of vision and requires remembering and dexterity for instillation, poor compliance is not uncommon (7). In addition we believe that instillation of drops disturbs the homeostasis of the natural tear film due to physical and chemical trauma due to large drop volume (50 microliters) hammering on the eye surface (which can only hold 7 to 10 microliters). Particularly washing away of the mucin layer that holds all the “good ingredients” in the tears is harmful to the ocular surface. Therefore, “dropless” treatment of dry eye is desirable.

Dextenza® (dexamethasone ophthalmic insert, Ocular Therapeutix Inc., Bedford, MA) is a corticosteroid intracanalicular insert approved by US-FDA in November 2018 for the treatment of post-surgical ocular inflammation and pain. It is inserted into the lower lacrimal punctum and into the canaliculus. A single insert releases a 0.4 mg dose of dexamethasone for up to 30 days following insertion. Dextenza® is resorbable and does not require removal. We hypothesize that Dextenza® could mimic short-term topical steroid use in a tapering manner in patients with clinically significant dry eye and show efficacy in improving its symptoms and signs, as was previously shown with other steroid preparations. If proven, the use of Dextenza® may shift paradigms in the management of the clinically significant ocular surface disease. To test this hypothesis, we propose to study the effects of Dextenza® in the treatment of clinically significant dry eye. This proposal has several strengths over a non-masked protocol:

- 1- We have identified a tear duct plug with a comparable size (size 0.5mm) that lasts 60-180 days (Vera90TM). This would serve as an excellent comparison to Dextenza and allow the study to be a double-masked design. Both devices are not visible at the slit-lamp once inserted.
- 2- The investigator enrolling the patient (inserting the study treatment versus the control treatment) will be different than the examining investigator for each patient to allow the study to be truly double masked.
- 3- Because each patient will have one Dextenza eye and one control eye, the efficacy and safety of the treatment will be fairly, effectively, and accurately assessed. The

“patient” related factors in this small scale study (such as difference in use of computers or sleep/wake hours, environmental factors such as humidity during this short-term study, or severity of ocular surface inflammation particularly whether underlying Sjögren’s syndrome is present or not, as well as the severity of evaporative component of the dry eye) will be comparable between the treatment and the control.

4- Also, this design allows both eyes of the same patients enrolled as study eyes thereby decreasing the sample size, hence the cost.

1.2.1 Rationale for Study Design

We determined the sample size using STATA Statistical Software (STATA Release 12.1; STATA Corp., College Station, TX). Standard deviations from previously published data sets were used for calculations (8).

Efficacy There will be two primary efficacy measures performed at day 28. The improvement in corneal staining score (using the OSS scale) and improvement in the most bothersome symptom (using the VAS scale between 0 to 100).

Efficacy Endpoint 1: Improvement in the corneal staining score measured using OSS scoring system (0-6). With a power of 80% and significance level of 0.05, 23 persons in each group (having both eyes eligible) need to be enrolled to detect a clinically significant 3 point difference in the mean corneal staining between the treated arm versus the sham arm at day 28.

Efficacy Endpoint 2: Improvement in most bothersome dry eye symptom as measured using VAS (0 to 100). With power of 80% and significance level of 0.05, 85 persons in each group (having both eyes eligible) need to be enrolled to detect a clinically meaningful 30 point difference in the most bothersome dry eye symptom Assuming that there will be a clinically significant 30% difference in the mean most bothersome symptom between the treated arm versus the sham arm at day 28.

One problematic issue in the field of dry eye is the lack of widely agreed upon core outcomes (9). It is currently not well known for example whether improving corneal staining is clinically meaningful and how much improvement would be necessary to make a difference in what the patient is experiencing. Our previous investigator initiated studies demonstrated that corneal fluorescein staining directly relates to impairment of visual function, and reduction in reading speed (10). The relationship is linear and for each 1 severity grade increase in corneal staining (0-6), we found an average of two words per minute reduction in reading speed, using iRest out loud testing and 10 words per minute reduction in reading speed using the sustained silent reading test. Therefore, perhaps corneal staining can be used as a clinically meaningful core outcome.

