DOSE/ROUTE/SCHEDULE:	Each patient's right eye will be randomized to receive either the treatment or the control. The left eye will automatically receive the alternative. For example if the right eye of the patient gets randomized to receive the study medication, left eye will automatically be the control eye. If the right eye gets randomized to receive the control treatment, the left eye will receive the study medication.
	Control eye will receive a sham treatment: commercially available tear duct plug without the dexamethasone (Vera90TM EXTENDED WEAR SYNTHETIC ABSORBABLE PUNCTAL PLUG made of E-Caprolactone-L-Lactide copolymer (PCL). Absorbs in 60 to 180 days. Size 0.5mm which is comparable to the study treatment)
	RESCUE MEDICINE: In patients with worsening of signs or symptoms, topical loteprednol 0.5% (Lotemax) drops up to 4 times a day, mimicking the usual practice, can be used at the discretion of the principle investigator.
	In patients with increased intraocular pressure (more than 5 points greater than baseline or more than 5 points higher than the fellow eye) treatment with topical beta blocker/betaxolol 0.5% (Betoptic) drops can be used 2 times a day to bring down the pressure at the discretion of the principle investigator.

Endpoint(s)

PRIMARY EFFICACY: Efficacy will be measured at 28 days.)

We have two co-primary end points:

- 1- Dry eye Sign: Corneal staining score measured using OSS scale on Day 28. The difference between the average corneal staining in the treated arm versus the average corneal staining in the sham arm will be compared statistically.
- 2- Patient reported symptom: Most bothersome symptom (any one of the (1)eye dryness, (2)eye discomfort, or (3)eye fatigue will be established as the most bothersome symptom at baseline for each eye) measured using visual analogue scale (0 to 100). The difference between the average most bothersome symptom in the treated arm versus the average most bothersome symptom in the sham arm will be compared statistically.

Secondary Efficacy:

We have two secondary end points:

- 1- Corneal staining responder analysis. Responder is defined as one full severity grade improvement in corneal staining. The percentage of subjects achieving 1 severity grade improvement in corneal staining (responders) in the treated arm versus sham arm will be compared statistically.

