4.1.1 Inclusion Criteria

A patient's study eye must meet the following criteria to be eligible for inclusion in the study:

- 1) Male or Female Age 18-100
- 2) Capacity to give informed consent
- 3) Ability to follow study direction and complete all study visits
- 4) A previous or current diagnosis of dry eye by an eye care specialist, whereas treatment is requiring the use of a topical steroid
- 5) Able to have a lacrimal plug placement into both lower puncta. If lower puncta are already plugged or cauterized/sealed, upper puncta will be used

- 6) Females of childbearing potential unwilling to use reliable form(s) of birth control throughout study period
- 7) Clinical diagnosis of dry eye syndrome (DES) or keratoconjunctivitis sicca (KCS), in which the following has been bilaterally documented in the ophthalmic and medical histories:
 - i. history/diagnosis of dry eye
 - ii. has taken or is on prescription drops (including but not limited to topical steroids, cyclosporine or lifitigrast)
- 8) Presence of all of the following in both eyes at Baseline (Day 1):
 - i. Total OSS of 3 or more with at least 2+ corneal staining (0-6)
 - ii. Unaesthetized Schirmer level of <10 mm at 5 minutes
 - iii. Presence of significant symptoms defined as 30mm or higher score of (1) eye dryness, or (2) eye fatigue, or (3) eye discomfort as measured using VAS, in both eyes.

At the baseline visit, the most bothersome symptom (of the three) will be determined and used as the main symptom outcome measure throughout the study.

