6.2 Primary and Secondary Endpoints

6.3 Primary Objective(s)

To determine the efficacy of dexamethasone insert through Day 28, as measured by –

- Improvement in corneal staining score in the treatment versus sham arm
- Improvement in worst/most bothersome symptom in the treatment versus control group

In addition

- % of patients with improvement of corneal staining score by one severity grade (clinically meaningful) in treatment versus control group
- % of patients with improvement of worst/most bothersome symptom by 30 points (clinically meaningful) in the treatment versus control group

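### The 3-point corneal target and the 23 persons per group do not fit together on a 0-6 score, and the target is neither justified nor reconciled with the one grade called clinically meaningful

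*Combined protocol and SAP*

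**What the plan says.** Section 1.2.1 (Efficacy Endpoint 1) names the outcome as "Improvement in the corneal staining score measured using OSS scoring system (0-6"). It gives the size as follows: "With a power of 80% and significance level of 0.05, 23 persons in each group (having both eyes eligible) need to be enrolled". The purpose of that number is stated as "to detect a clinically significant 3 point difference in the mean corneal staining", comparing treated with sham eyes at Day 28. No SD is printed; the text says only "Standard deviations from previously published data sets were used for calculations (8"). The same section sizes the symptom co-primary at 85, and the synopsis and section 4.1 plan 85 patients with one treated and one control eye each.

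Section 6.3 lists, as a percentage of patients, "improvement of corneal staining score by one severity grade (clinically meaningful) in treatment versus control group". The synopsis and section 2.1 use the same one-grade responder threshold. Section 1.2.1 treats one severity grade as one step of the 0-6 score when it reports reading speed per grade.

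Section 4.1.1, item 8.i, requires in both eyes at baseline "Total OSS of 3 or more with at least 2+ corneal staining (0-6"). For the analysis, the synopsis says: "The difference between the average corneal staining in the treated arm versus the average corneal staining in the sham arm will be compared statistically".

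**The concern.** The planning difference for a co-primary endpoint should be one that the sponsor can defend as relevant and reachable, and the sample size should follow from it. Here a mean separation of half the scale is called clinically significant without support, while another section attaches clinical meaning to one grade. The entry rule admits eyes at 2, which cannot improve by 3. With no SD given, the reader cannot see how 3 points leads to 23 persons.

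Two things are at stake. If the trial finds a mean benefit of about one grade, the protocol can be cited both for and against its relevance, and that dispute would arise after unmasking. And the 23 tells the reader nothing reliable about the power of the corneal comparison.

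**Working it through.** **Inputs.** From section 1.2.1: difference 3, n = 23 per group, power 80%, alpha 0.05, scale 0-6. From section 4.1.1: corneal score at entry 2 or more. From the synopsis: 85 patients, fellow-eye control. Assumed: two-sided alpha (sidedness is not stated), so z = 1.960 + 0.842 = 2.802; within-pair SDs of 1.5 to 2.5 (none is given); 85 evaluable pairs (no dropout allowance is stated).

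**1. Can the plan's 23 be reproduced?** With no SD stated, solve for it.

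- Two-sample: n = 2(2.802 × SD / difference)², so SD = 3 × √(23/2) / 2.802 = 3.63 (3.55 with the t distribution).
- Paired: SD of differences = 3 × √23 / 2.802 = 5.14 (4.91 with t).

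**2. What can the scale produce?**

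- A score bounded by 0 and 6 with mean m has SD at most √(m(6 − m)), which peaks at 3.0 when m = 3. An SD of 3.55 to 3.63 is out of reach.
- Even at SD 3.0, n = 2(2.802 × 3/3)² = 15.7, so 16 per group. If the arm means really differ by 3 (for example 1.5 and 4.5), the largest average SD is √(1.5 × 4.5) = 2.60, and n is about 12.
- A paired difference lies between −6 and 6. With mean 3 its SD is at most √((6 − 3)(3 + 6)) = 5.20. An SD of 4.9 to 5.1 would need almost every patient at one of the two extremes, which is not credible.

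The 23 is therefore not reproduced for 3 points by either formula with a credible SD.

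**3. What would give 23?** A 1-point difference with SD 1.2: 2(2.802 × 1.2)² = 22.6, so 23. This is a numerical match only.

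**4. Is a 3-point separation reachable?** Let B be the mean baseline, c the mean improvement in sham eyes and r the mean score left in treated eyes at Day 28. The separation is (B − c) − r. For it to equal 3, B = 3 + c + r. If sham eyes do not worsen (c ≥ 0), B must be at least 3, and B = 3 is enough only if every treated eye clears to zero. If sham eyes, which receive a punctal plug, improved by 0.5 (an assumption), B would have to be at least 3.5.

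**5. Power for one grade.** Noncentral t, paired, two-sided 0.05, at assumed within-pair SDs:

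| Within-pair SD | 23 pairs | 85 pairs | Detectable difference, 85 pairs, 80% power |
|---|---|---|---|
| 1.5 | 86% | >99% | 0.46 |
| 2.0 | 63% | >99% | 0.62 |
| 2.5 | 45% | 95% | 0.77 |

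With 85 pairs, power for one grade stays at 80% or more up to a within-pair SD of 3.25.

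**The case against.** The strongest defence has four parts.

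- **Different quantities.** Three points is a difference between arm means; one grade is a within-patient responder cut-off. They need not be equal. The reading-speed result is a slope per grade, not a threshold, and section 1.2.1 itself says that the amount of staining improvement that matters is not well known. This stands. A reader might infer that the protocol contradicts itself and that 3 points is simply wrong; the text shows only that the target is unjustified and unreconciled.
- **The floor binds few or many eyes, unknown which.** The entry rule sets a minimum, so eyes may enter at 2 to 6, and only those at exactly 2 are limited to a gain of 2. The baseline distribution is not given, and worsening in sham eyes would widen the gap. This stands too: a reader might infer that 3 points is impossible, but it is only implausible.
- **No practical harm.** The symptom endpoint sets enrolment at 85, and the arms are merely to be compared, with no 3-point success criterion. A reader might infer that a one-grade result would count as a failure. It would not: with 85 pairs, an observed one-grade difference is significant at two-sided 0.05 up to a within-pair SD of about 4.6 (√85 / 1.989).
- **The calculation may have used another quantity.** The 3.0 ceiling holds for the Day 28 score, which section 1.2.1 names for the planned difference. Improvement from baseline could range from −4 (2 to 6) to 6 (6 to 0), so its SD is bounded by 5 rather than 3. That leaves 3.6 mathematically possible for a change score, but still very large on this scale. It is one more reason to print the SD and the quantity it belongs to.

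None of this explains how 3 points and 23 persons belong together as written.

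**Conclusion.** The point holds in a limited form. The 3-point target is half the scale, has no justification in the documents and is left beside a one-grade benchmark without explanation. For the Day 28 score, 3 points and 23 per group require a two-sample SD of about 3.6 against a maximum of 3.0, or an SD of differences of 4.9 to 5.1 against a ceiling of 5.2. At least one figure in a co-primary design statement is therefore untenable as written. It is tempting to conclude that 3 was written for 1, since 1 point with SD 1.2 gives 23; the documents cannot settle this.

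The consequence is for interpretation and for the record, not for enrolment. The planned 85 pairs have 95% power or more for one grade at assumed within-pair SDs up to 2.5. This rests on two-sided alpha, a paired analysis and 85 evaluable pairs. The bounds in the check of the 23 need no assumed SD.

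**What to change.** Revise the Efficacy Endpoint 1 paragraph in section 1.2.1:

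1. Check the 3 points and the 23 persons against the original sample-size calculation, and correct or withdraw them. Do not delete the 23 before this check, since it is the main clue to what was calculated.
2. State the SD, its source, whether it belongs to the Day 28 score, the change or the within-patient difference, and that the comparison is paired and two-sided.
3. Restate the corneal design as the power of the planned 85 pairs for a one-grade mean difference: at least 80% if the within-pair SD is 3.25 or less, with a detectable difference of about 0.46 to 0.77 grade at assumed within-pair SDs of 1.5 to 2.5.
4. Add a sentence on how the mean difference relates to the one-grade responder threshold in the synopsis and sections 2.1 and 6.3. If a larger mean target is kept, justify it.

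The cost is one paragraph and a look at the original calculation. No more patients are needed.

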Safety and Efficacy of Dexamethasone Ophthalmic Insert (Dextenza®) in the Management of
Clinically Significant Dry Eye

NCT04498468

Date: September 21, 2020

Safety and Efficacy of Dextenza in Dry Eye (V3)

Clinical Study Protocol

Safety and Efficacy of Dexamethasone Ophthalmic Insert (Dextenza®) in the Management of Clinically Significant Dry Eye

Compound:	Sustained Release Dexamethasone, 0.4 mg.
Study Name:	Safety and Efficacy of Dexamethasone Ophthalmic Insert (Dextenza®) in the Management of Clinically Significant Dry Eye.
Clinical Phase:	Phase IV, prospective, masked trial.
Date of Issue:	September 21, 2020
Principal Investigator:	[name].
Sub Investigators:	[name]. [name], OD.
Site Name & Location:	Ocular Surface Diseases and Dry Eye Clinic, The Wilmer Eye Institute, The Johns Hopkins University School Of Medicine, Baltimore, Maryland.

CLINICAL STUDY PROTOCOL SYNOPSIS

TITLE	Safety and Efficacy of Dexamethasone Ophthalmic Insert (Dextenza®) in the Management of Clinically Significant Dry Eye.
SITE LOCATION(S)	Ocular Surface Diseases and Dry Eye Clinic, The Wilmer Eye Institute, The Johns Hopkins University School Of Medicine, Baltimore, Maryland.
PRINCIPAL INVESTIGATOR	[name].
OBJECTIVE(S)	To determine efficacy and safety profile of dexamethasone 0.4mg lacrimal insert in dry eye related ocular surface inflammation.
STUDY DESIGN	Prospective, double-masked, interventional clinical trial.
STUDY DURATION	42 Days per patient, There will be 5 visits (run in, Day 1, 14, 28, and 42) with 12 months of active enrollment. Start-up period (finalizing the protocol and case report forms, obtaining approvals from institutional review board, etc): 3 months. Enrollment period: 12 months. Close-out (data completion and lock, statistical analyses, and multiple manuscript preparations etc): 3 months. Interim data analysis at 6 months. Total of 18 months
ESTIMATED STUDY COMPLETION DATE	December 31, 2021
POPULATION	Adult patients with significant dry eye or keratoconjunctivitis sicca, requiring topical steroid treatment.
Sample Size:	85 patients [1 treatment eye/1 control eye = 170 eyes] will be enrolled at a single site.
Treatment(s)	

Study Drug	Sustained release dexamethasone, 0.4 mg

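### Section 1.2.1: the stated sample sizes, differences and 80% power cannot all hold for Day 28 scores on either co-primary, and the VAS target is given both as 30 points and as 30%

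*Combined protocol and SAP*

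**What the plan says.** The Synopsis sets enrolment: "85 patients [1 treatment eye/1 control eye = 170 eyes] will be enrolled at a single site". Each patient contributes one treated and one sham eye.

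Section 1.2.1 justifies the number endpoint by endpoint, each at 80% power and significance level 0.05:

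- **Corneal staining (0–6):** "23 persons in each group (having both eyes eligible) need to be enrolled to detect a clinically significant 3 point difference" between the arms at Day 28.
- **VAS, most bothersome symptom (0–100):** "85 persons in each group (having both eyes eligible) need to be enrolled to detect a clinically meaningful 30 point difference". The same sentence continues: "Assuming that there will be a clinically significant 30% difference in the mean most bothersome symptom". It does not say what the 30% is a percentage of.

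The section says that SDs came from published data (its reference 8), but prints no SD, test, sidedness or between-eye correlation.

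On the quantity analysed, the Synopsis names the first co-primary as "Corneal staining score measured using OSS scale on Day 28" and the second comparison as "The difference between the average most bothersome symptom in the treated arm versus the average most bothersome symptom in the sham arm". Sections 1.2.1, 2.1 and 6.3 label the same endpoints as improvement.

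**The concern.** Any score confined to a range has a largest possible SD, equal to half the range. The stated n, difference and power fix the SD that must have been used, so they can be tested without seeing the cited source. Here the SDs they imply exceed those limits on both scales.

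The VAS figure of 85 sets enrolment, since 23 is not binding, and this paragraph is its only justification. A reader cannot tell whether 85 was derived for 30 points, for a smaller difference expressed as a percentage of a mean, or for change from baseline. The trial's design sensitivity for symptoms is therefore unknown.

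**Working it through.** **Inputs from the documents.** n = 85 per group with difference 30 on 0–100; n = 23 per group with difference 3 on 0–6; power 80%; significance level 0.05 (all section 1.2.1). Entry requires VAS of at least 30 and corneal staining of at least 2 (section 4.1.1). Two-sided testing is assumed because sidedness is not stated.

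**The plan's figures** cannot be reproduced forwards, because no SD is given. I solve for the SD instead, with k = (1.960 + 0.842)² = 7.849.

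**1. Two-group comparison of Day 28 scores.** SD = √(n·d² / 2k).

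- VAS: √(85 × 900 / 15.698) = 69.8 (69.4 by noncentral t).
- Staining: √(23 × 9 / 15.698) = 3.63 (3.55 by t).

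The largest possible SD is 100/2 = 50 and 6/2 = 3. If the arm means differ by 30 or by 3, the largest pooled SD is lower: √(35 × 65) = 47.7 and √(1.5 × 4.5) = 2.60. Both implied SDs are out of reach. One-sided 0.05 widens the gap (78.7 and 4.09). Significance level 0.025 (63.4 and 3.30), 90% power (60.3 and 3.14) or a 30% drop-out allowance inside n (58.4 and 3.04) does not close it.

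**2. Paired comparison of Day 28 scores.** SD of differences = √(n·d² / k).

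- VAS: 98.7 (t 97.6), against a maximum of √(70 × 130) = 95.4. Not possible.
- Staining: 5.14 (t 4.91), against √(3 × 9) = 5.20. Possible, but the between-eye correlation must be about 1 − 5.14² / (2 × 6.75) = −0.95 (t-based −0.78), even at the largest pooled SD. Section 1.2 argues the reverse, that patient factors "as well as the severity of evaporative component of the dry eye) will be comparable between the treatment and the control".

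**3. Change from baseline.** With entry at 30 or more and 2 or more, improvement can run from −70 to 100 and from −4 to 6. The largest pooled SDs, given the stated differences, are √(70 × 100) = 83.7 and √(3.5 × 6.5) = 4.77. The implied 69.8 and 3.63 are very large but not excluded.

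**4. VAS target as 30% of the sham mean m** (m is assumed). Implied SD at n = 85, against the largest pooled SD √(85m − 0.745m²):

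| m | Target (points) | Implied SD | Largest SD |
|---|---|---|---|
| 30 | 9 | 20.9 | 43.4 |
| 40 | 12 | 27.9 | 47.0 |
| 50 | 15 | 34.9 | 48.9 |
| 60 | 18 | 41.9 | 49.2 |
| 70 | 21 | 48.9 | 48.0 |

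This reading is possible up to a mean of about 69. If 30% means 30% of the 0–100 scale, it is 30 points again and step 1 applies.

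**5. What the stated point targets need on Day 28 scores** (t-tests, 80% power).

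| | VAS, 30 points | Staining, 3 points |
|---|---|---|
| Two-group, largest SD (50; 3) | 45 per group | 17 per group |
| Two-group, largest pooled SD (47.7; 2.60) | 41 per group | 13 per group |
| Paired, correlation ≥ 0 | at most 42 pairs | at most 14 pairs |
| Power at stated n, two-group, SD 50 or 3 | 97.3% (n = 85) | 91.2% (n = 23) |

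The paired row uses SDs of differences of at most √2 × 47.7 = 67.5 and √2 × 2.60 = 3.67.

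**6. What 85 pairs detect.** By paired t-test at 80% power, 0.307 times the SD of the paired difference, which is SD × √(2(1 − correlation)). With 72 pairs (15% drop-out assumed: 85 × 0.85 = 72.25) the factor is 0.335. For illustration, with assumed correlations of 0.3–0.7:

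| | 85 pairs | 72 pairs |
|---|---|---|
| VAS, assumed SD 20–35 | about 5–13 points | about 5–14 points |
| Staining, assumed SD 1–2 | 0.24–0.73 points | 0.26–0.79 points |

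**The case against.** The impossibility depends on analysing Day 28 scores, and section 1.2.1 itself speaks of improvement. On change from baseline the implied SDs are not ruled out. With a paired analysis of change, they fit at between-eye correlations of 1 − 98.7² / (2 × 83.7²) = 0.30 for VAS and 1 − 5.14² / (2 × 4.77²) = 0.42 for staining. For VAS, the endpoint that sets N, reading 30% as a share of a mean makes 85 consistent, so the proven defect there may be wording rather than arithmetic. The SDs lie in a source that cannot be seen here. In any case the trial is larger than its stated targets require, and restating what 85 pairs detect does not show why 85 was chosen.

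Much of this stands as a limit. The conflict is proved only for the stated point differences on Day 28 scores, the cause cannot be identified, and no power is lost. It does not remove the point. The Synopsis compares arm averages and puts staining on Day 28, and section 1.2.1 places both differences at Day 28. The change-from-baseline escape, paired or not, needs SDs close to the largest that the scales allow. No source could supply a Day 28 SD above the bound. The percentage reading only confirms that the VAS target is ambiguous, and does nothing for staining, which has no percentage wording. The back-calculation objection is fair: the original rationale can come only from the sponsor's own inputs, which is why the fix asks for them first.

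**Conclusion.** The concern holds. For a two-group comparison of Day 28 scores, the printed n, difference and 80% power conflict for both co-primaries: implied SD 69.8 against a ceiling of 50, and 3.63 against 3. Pairing does not cure VAS, and cures staining only at an implausible correlation. Separately, the VAS target has two wordings that can differ by a factor of about 1.7 to 3.3 (30 points against 18 to 9, for an assumed mean of 60 to 30).

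The bounds rest on the scale ranges and on the printed n, difference, level and power, with no assumed SD. They do not extend to change from baseline. The error runs towards excess size, so this is a defect in the justification of N = 85 and not a threat to power at the stated targets. It should be corrected.

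**What to change.** Keep N = 85 patients and rewrite section 1.2.1:

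1. State the SDs used, the sidedness, and whether the outcome is the Day 28 score or change from baseline.
2. Base the calculation on the paired fellow-eye comparison, with an assumed between-eye correlation.
3. For each co-primary, report the difference that 85 pairs detect at 80% power (0.307 × SD of the paired difference), and again after expected drop-out (0.335 × for 72 pairs, if 15% is assumed).
4. Keep one VAS target. If it is a percentage, say of what, and give the resulting points.

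Separately, reconcile the symptom responder threshold: it is 30% in the Synopsis (Secondary Efficacy) and section 2.1, but 30 points in section 6.3. For a baseline of 40, those are 12 and 30 points.

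The cost is one rewritten paragraph and one aligned definition. No patients are added and the co-primary endpoints do not change, though the stated detectable differences may.
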